### 3.8.4 Safety Analysis

The eDMC has responsibility for assessment of overall risk/benefit. When prompted by safety concerns, the eDMC can request corresponding efficacy data. eDMC review of efficacy data to assess the overall risk/benefit to study participants will not require a multiplicity adjustment typically associated with a planned efficacy IA.

### 3.9 Sample Size and Power Calculations

The study will randomize 432 participants in a 1:1 ratio into the MK-4280A arm (Arm A) and the standard of care arm (Arm B). OS is the primary endpoint for the study, with PFS and ORR as the key secondary endpoints.

For the OS endpoint, based on a target number of 386 events and 1 IA at approximately 80% of the target number of events, the study has approximately 93.5% power to detect a HR of 0.7 at the initially allocated  $\alpha=0.025$  (1-sided).

For the PFS endpoint, based on a target number of 419 events at the IA (final PFS analysis), the study has approximately 99% power to detect a HR of 0.65 at the reallocated  $\alpha=0.0125$  (1-sided) if only OS hypothesis is rejected.

Based on the 432 participants with at least approximately 10 months of follow-up, the power of the ORR testing at the reallocated  $\alpha=0.0125$  (1-sided) if only OS hypothesis rejected is approximately 97% to detect a 10-percentage point difference between an underlying 2% ORR in the control arm (Arm B) and a 12% ORR in the experimental arm (Arm A).

Note that the above OS and PFS power calculations are based on a constant HR assumption.

[figure not shown]
Based on CORRECT, RE COURSE, and SUNLIGHT studies (Section 4.2.1.1 of protocol), the above sample size and power calculations for OS and PFS assume the following:

- OS follows an exponential distribution with a median of 7.5 months for the control group.
- PFS follows an exponential distribution with a median of 2 months for the control group.
- Enrollment period of 12 months with enrollment ramp-up over first 2 months.
- An annual dropout rate of 2% and 5% for OS and PFS, respectively
- A follow-up period of 22 and 10 months and for OS and PFS, respectively, after the last participant is randomized.

The sample size and power calculations were performed using R (“gsDesign” package).

### **3.10 Subgroup Analyses and Effect of Baseline Factors**

CCI

### **3.11 Compliance (Medication Adherence)**

Drug accountability data for study treatment will be collected during the study. Any deviation from protocol-directed administration will be reported.

### 3.12 Extent of Exposure

Extent of Exposure for a participant is defined as the number of cycles and number of days for which the participant receives the study intervention. Summary statistics will be provided on the extent of exposure for the overall study intervention for the APaT population.

## 4. APPENDIX

### 4.1 REGION/COUNTRY-SPECIFIC REQUIREMENTS

#### 4.1.1 China-specific Requirements

This section outlines the statistical analysis strategy and procedures for China subpopulation (including China participants randomized in the global portion and China extension portion). China refers to China mainland in this section.

The purpose of the China extension portion is to ensure an adequate sample size to evaluate the consistency of effect for efficacy and safety between the China subpopulation and the global population. Country-specific analyses may also be conducted per local regulatory requirement.

After the enrollment for the global portion is completed, participants in China will continue to be enrolled in a 1:1 ratio into the MK-4280A arm and the standard of care arm until the sample size for the China subpopulation reaches approximately 94 in total (global and China extension portion combined).

The China extension portion will be completed at about 14 months after enrollment of China extension is completed.

Key elements of the statistical analysis plan for China subpopulation are summarized below. More details are provided in following sections.

Analysis Populations	Efficacy: ITT China subpopulation (including China participants randomized in the global portion and the China extension portion) Safety: APaT China subpopulation (including China participants randomized in the global portion and the China extension portion who received at least one dose of study treatment)
Efficacy Endpoint(s)	Efficacy endpoints are the same as described in Section 3.4.1
Safety Endpoint (s)	Safety endpoints are the same as described in Section 3.4.2
PRO Endpoint(s)	Separate PRO analysis for the China subpopulation is not applicable

[figure not shown]
Statistical Methods for Efficacy Analyses	No formal hypothesis testing is planned, and no multiplicity adjustment will be applied to the analysis for China subpopulation. Unstratified methods will be used for China subpopulation analyses.
Statistical Methods for Safety Analyses	Safety analyses for China subpopulation are the same as those for the global portion as described in Section 3.6.2 if applicable.
Summaries of Baseline Characteristics and Demographics	They are the same for China subpopulation as those for the global portion as described in Section 3.6.4
Analyses Timing	CCI
Hypotheses and Multiplicity	
Sample Size Calculations	

#### **4.1.1.1 Responsibility for Analyses/In-House Blinding**

For all China participants, including participants randomized in the global portion and the China extension portion, patient level treatment randomization information will be blinded for a designated team for China analysis within the Sponsor until the China extension portion database lock is achieved.

#### **4.1.1.2 Analyses Timing**

CCI

#### **4.1.1.3 Sample Size Calculations**

After the completion of global portion enrollment, the China extension portion will continue to enroll participants and randomize eligible participants until the sample size for the overall randomized China subpopulation reaches approximately 94. Participants from China enrolled in the China extension portion of this study after completion of the global enrollment will not be included in the primary analysis population for the global portion.

The China extension portion will complete at about 14 months after the enrollment of China extension is completed. CCI

CCI

CCI

## 4.2 Technical Details for cLDA Model

The cLDA model assumes a common mean across treatment groups at baseline and a different mean for each treatment at each of the post-baseline time points. In this model, the response vector consists of baseline and the values observed at each post-baseline time point. Time is treated as a categorical variable so that no restriction is imposed on the trajectory of the means over time. The cLDA model is specified as follows:

$$E(Y_{ijt}) = \gamma_0 + \gamma_{jt}I(t > 0) + \beta X_i, j = 1, 2, 3, \dots, n; t = 0, 1, 2, 3, \dots, k$$

where  $Y_{ijt}$  is the PRO score for participant  $i$ , with treatment assignment  $j$  at visit  $t$ ;  $\gamma_0$  is the baseline mean for all treatment groups,  $\gamma_{jt}$  is the mean change from baseline for treatment group  $j$  at time  $t$ ;  $X_i$  is the stratification factor (binary) vector for this participant, and  $\beta$  is the coefficient vector for stratification factors. An unstructured covariance matrix will be used to model the correlation among repeated measurements. If the unstructured covariance model fails to converge with the default algorithm, then Fisher scoring algorithm or other appropriate methods can be used to provide initial values of the covariance parameters. In the rare event that none of the above methods yield convergence, a structured covariance such as Toeplitz can be used to model the correlation among repeated measurements. In this case, the asymptotically unbiased sandwich variance estimator will be used. The cLDA model implicitly treats missing data as missing at random (MAR).

## 4.3 Technical Details for Minimal Spending Approach

Below are the technical details for the minimum spending approach.

The Lan-DeMets spending function to approximate an O'Brien-Fleming bound is defined as

$$f(t; \alpha) = 2 - 2\Phi\left(\frac{\Phi^{-1}\left(1 - \frac{\alpha}{2}\right)}{\sqrt{t}}\right)$$

where  $t$  in  $f(t; \alpha)$  is the spending time, which is not necessarily information fraction or actual time.

The test statistics  $Z_i$  at each analysis  $i$  is assumed to follow a multivariate normal distribution with expectations  $E(Z_i) = \theta\sqrt{I_i}$  and covariances  $Cov(Z_i, Z_j) = \sqrt{I_i/I_j}$  where  $\theta$  is the treatment effect difference of interest and  $I_i$  is the actual statistical information available based on the actual observed event number.

To illustrate how the minimum spending approach is implemented, examples with one hypothetical scenarios where events accrue slower and faster than expected are given below for the OS analyses with the total alpha of 2.5% (initially allocated). There are 2 planned analyses for OS at IA and FA, respectively.

**IA boundary calculation:**

For the OS interim analysis, the p-value boundary is the same as alpha spending  $\alpha_1$  determined from the Lan-DeMets spending function. At the time of the analysis, 309 events are expected over the target 386 events at the FA.

- Hypothetical scenario 1 (events accrue slower than expected): 296 events are observed. The spending time is calculated as  $t = 296/386 = 77\%$  and p-value boundary = 0.0122
- Hypothetical scenario 2 (events accrue faster than expected): 320 events are observed. The spending time is calculated as  $t = 309/386 = 80\%$  and p-value boundary = 0.0122

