Multiplicity	The overall type I error over the primary and secondary hypotheses is strongly controlled at 2.5% (1-sided), CCI [REDACTED] By using the graphical approach of Maurer and Bretz [Maurer, W. and Bretz, F. 2013], if one hypothesis is rejected, the alpha will be shifted to other hypotheses.
Sample Size and Power	CCI [REDACTED]
Abbreviations: APaT = all participants as treated; BICR = blinded independent central review; CI = confidence interval; DMC = data monitoring committee; eDMC = external data monitoring committee; FAS = full-analysis set; HR = hazard ratio; ITT = intent to treat; M&N = Miettinen and Nurminen; ORR = objective response rate; CCI [REDACTED]; PFS = progression free survival; SOC = standard of care	

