### 3.8.1 Overall Survival

The study will test OS at IA and FA. Following the multiplicity strategy as outlined in [Figure 1](#), the OS hypothesis will be tested at  $\alpha=0.025$ . [Table 9](#) shows the bounds and boundary properties for OS hypothesis testing derived using a Lan-DeMets spending function approximating O'Brien-Fleming bounds.

Table 9 Efficacy Boundaries and Properties for Overall Survival Analyses

Analysis	Value	$\alpha=0.025$
IA: 80%*	Z	2.2504
N: 432	$p$ (1-sided) a	0.0122
Events: 309	HR at bound b	0.7738
Month: 21	P(Cross) if HR=1 c	0.0122
	P(Cross) if HR=0.7 d	0.8123
FA	Z	2.0249
N: 432	$p$ (1-sided) a	0.0214
Events: 386	HR at bound b	0.8135
Month: 33	P(Cross) if HR=1 c	0.0250
	P(Cross) if HR=0.7 d	0.9350

Abbreviations: HR=hazard ratio; IA=interim analysis, FA=final analysis.  
 The number of events and timings are estimated.  
 \*Percentage of total planned events at the interim analysis.  
a $p$  (1-sided) is the nominal  $\alpha$  for group sequential testing.  
bHR at bound is the approximate HR required to reach an efficacy bound.  
cP(Cross if HR=1) is the probability of crossing a bound under the null hypothesis.  
dP(Cross if HR=0.7) is the probability of crossing a bound under the alternative hypothesis.

The bounds provided in the table above are based on the assumptions that the expected number of events at IA and FA are 309 and 386, respectively. At the time of an analysis, the observed number of events may differ substantially from the expected. To avoid overspending at an IA

and leave reasonable  $\alpha$  for the FA, the minimum  $\alpha$  spending strategy will be adopted. At an IA, the information fraction used in Lan-DeMets spending function to determine the alpha spending at the IA will be based on the minimum of the expected information fraction and the actual information fraction at each analysis. Specifically,

- In the scenario that the events accrue slower than expected and the observed number of events is less than the expected number of events at a given analysis, the information fraction will be calculated as the observed number of events at the IA over the target number of events at FA.

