- In the scenario that the events accrue faster than expected and the observed number of events exceeds the expected number of events at a given analysis, then the information fraction will be calculated as the expected number of events at the IA over the target number of events at FA.

The final analysis will use the remaining Type I error that has not been spent at the earlier analysis. The event counts for all analyses will be used to compute correlations.

Of note, while the information fraction used for alpha spending calculation will be the minimum of the actual information fraction and the expected information fraction, the correlations required for deriving the bounds will still be computed using the actual information fraction based on the observed number of events at each analysis over the target number of events at FA.

The minimum spending approach assumes timing is not based on any observed Z-value and thus the Z test statistics used for testing conditioned on timing are multivariate normal. Given the probabilities derived with the proposed spending method, the correlations based on actual event counts are used to compute bounds that control the Type I error at the specified alpha level for a given hypothesis conditioned on the interim analysis timing. Since this is true regardless of what is conditioned on, the overall Type I error for a given hypothesis unconditionally is controlled at the specified level. By using more conservative spending early in the study, power can be retained to detect situations where the treatment effect may be delayed.

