**FA boundary calculation:**

The alpha spending at the FA is  $\alpha - \alpha_1$ . FA boundary ( $C_2$ ) is solved from  $P(Z_2 \geq C_2, Z_1 < C_1 | H_0) = \alpha - \alpha_1$ , with test statistics  $Z_1$  and  $Z_2$  being multivariate normal and correlations based on observed event numbers.

The table below summarizes the boundary properties of the hypothetical scenarios, together with the planned scenario.

Value	Planned scenario	Hypothetical scenario 1 (events accrue slower)	Hypothetical scenario 2 (events accrue faster)
IA: Month: 21			
Events (I.F.)	309 (80%)	296 (77%*)	320 (80%*)
Z	2.2504	2.2504	2.2504
p (1-sided)	0.0122	0.0122	0.0122
HR at bound	0.7738	0.7698	0.7776
P(Cross) if HR=1	0.0122	0.0122	0.0122
P(Cross) if HR=0.7	0.8123	0.7933	0.8263
FA: Month: 33			
Events	386	375	395
Z	2.0249	2.0289	2.0212
p (1-sided)	0.0214	0.0212	0.0216
HR at bound	0.8135	0.8110	0.8160
P(Cross) if HR=1	0.0250	0.0250	0.0250
P(Cross) if HR=0.7	0.9350	0.9276	0.9339
Information fraction is the minimum of the expected information fraction and the actual information fraction used for the alpha spending calculation. The actual information fraction based on the observed number of events is used for computing correlations needed to derive the group sequential bounds.			

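### SAP Section 4.3: the slow-accrual OS example states a 77% spending time but prints the 80% interim boundary (p 0.0122 instead of 0.0105)

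*SAP*

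**What the plan says.** Section 3.8.1 adopts minimum alpha spending for OS. If events accrue slowly, "the information fraction will be calculated as the observed number of events at the IA over the target number of events at FA". The section then restates the rule generally: "the information fraction used for alpha spending calculation will be the minimum of the actual information fraction and the expected information fraction". Correlations between the two looks use the observed event counts.

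Section 4.3 gives the Lan-DeMets O'Brien-Fleming-type spending function and says that the interim p-value boundary equals the alpha spent. It then offers worked examples, whose purpose is stated as "To illustrate how the minimum spending approach is implemented", "for the OS analyses with the total alpha of 2.5% (initially allocated").

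- Scenario 1 (slow accrual): "296 events are observed. The spending time is calculated as" 296/386 = 77%, "and p-value boundary = 0.0122".
- Scenario 2 (fast accrual): 320 events are observed, the spending time is held at 309/386 = 80%, and the boundary is again 0.0122.

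The table that follows labels scenario 1 as 296 events with an information fraction of 77%, but gives it the same interim Z (2.2504) and p (0.0122) as the planned case. Its footnote reads: "Information fraction is the minimum of the expected information fraction and the actual information fraction used for the alpha spending calculation".

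**The concern.** The spending function increases strictly with t, and the interim boundary is the alpha spent. Spending times of 77% and 80% therefore cannot share a boundary. Scenario 1 is also the only example in which the spending time departs from 80%, so it is the only one that could show the rule changing the spend, and it does not.

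At stake is the rejection threshold for the sole primary endpoint. If the interim is run clearly short of 309 events, the document supports one threshold by its rule and a more lenient one by its example, and the final-analysis bound shifts the other way. Rejecting OS also releases alpha to PFS and ORR (Section 3.8), so the choice carries through to the key secondary tests.

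**Working it through.** **Inputs.** Total OS alpha is 0.025, one-sided (Sections 3.1 and 4.3). Planned events are 309 at the interim and 386 at the final analysis (Table 9). Scenario 1 has 296 and 375 events, and scenario 2 has 320 and 395 (Section 4.3 table). Power is at HR 0.7.

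**Formulas.**
- Alpha spent: f(t) = 2 − 2Φ(Φ⁻¹(1 − 0.025/2)/√t), with Φ⁻¹(0.9875) = 2.2414.
- Interim bound: C₁ = Φ⁻¹(1 − f(t)).
- Final bound: C₂ solves P(Z₁ < C₁, Z₂ ≥ C₂) = 0.025 − f(t), with correlation √(interim events/final events).
- HR at bound: exp(−2C/√events).
- Power: normal drift of −ln(0.7)/2 × √events at each look.

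**Step 1: the planned boundary reproduces.** At t = 0.80, 2.2414/√0.80 = 2.5060, so f = 0.01221 and Z = 2.2504, as printed. The exact fraction 309/386 = 0.8005 gives f = 0.01224 and Z = 2.2495.

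**Step 2: scenario 1 at its stated spending time.**
- t = 296/386 = 0.7668: 2.2414/√0.7668 = 2.5596, f = 0.01048, Z = 2.3087.
- t = 0.77 as rounded: f = 0.01064, Z = 2.3030.
- t = 296/375 (another possible denominator): f = 0.01164.

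None of these gives 0.0122. Rounding does not explain the figure.

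**Step 3: where the printed column comes from.** Z is fixed at 2.2504 with 296 and 375 events in one calculation, and the rule is applied in the other.

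| Scenario 1 | Printed | Z fixed at 2.2504 | Rule, t = 296/386 |
|---|---|---|---|
| Interim Z | 2.2504 | 2.2504 | 2.3087 |
| Interim p and P(cross) if HR=1 | 0.0122 | 0.0122 | 0.0105 |
| Interim HR at bound | 0.7698 | 0.7698 | 0.7646 |
| Interim P(cross) if HR=0.7 | 0.7933 | 0.7933 | 0.7762 |
| Final Z | 2.0289 | 2.0289 | 2.0096 |
| Final p | 0.0212 | 0.0212 | 0.0222 |
| Final HR at bound | 0.8110 | 0.8110 | 0.8126 |
| Final power if HR=0.7 | 0.9276 | 0.9276 | 0.9290 |
| Total alpha | 0.0250 | 0.0250 | 0.0250 |

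Every printed value matches the 80% spend.

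**Step 4: size of the discrepancy.** The example spends 0.01221/0.01048 = 1.17 times the alpha that the rule allows at the interim. It leaves 0.0250 − 0.0122 = 0.0128 for the final analysis, against 0.0250 − 0.0105 = 0.0145. With 296 events, the chance that the interim Z falls between 2.2504 and 2.3087 is 1.7% at HR 0.7, 2.2% at HR 0.8 and 0.17% at HR 1. If the example's interim bound (2.2504) were followed by the rule's final bound (2.0096), total one-sided alpha would be 0.0258.

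**Step 5: scenario 2.** Fixing Z at 2.2504 with 320 and 395 events reproduces 0.7776, 0.8263, 2.0212, 0.0216 and 0.8160 as printed. Final power comes to 0.9399, against 0.9339 printed. The printed value is also implausible on its face: it lies below the planned 0.9350 despite more events at both looks.

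**The case against.** The rule itself is clear. Section 3.8.1 states it twice, the table footnote repeats it, and the scenario 1 bullet even computes the right spending time. The scenarios are labelled hypothetical, and the real bounds are to be derived from actual event counts. A statistician who follows Section 3.8.1 would not take 0.0122 from an appendix. Table 8 also requires about 309 events and about 10 months of follow-up before the interim, and its explicit allowance for falling short of target events concerns only the final analysis. Even with 296 events the disputed band is narrow, final power moves by only 0.0014, and total alpha is kept if the printed pair is used throughout.

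All of this is fair, and it limits the practical consequence. It does not remove the error. The event count in Table 8 is approximate, and Section 3.8.1 expressly provides for an interim with fewer events than expected. The example is the document's only numerical demonstration of that case, and its threshold is wrong. The protection of total alpha also depends on not mixing the example's interim bound with the rule's final bound. The scenario 2 power cell drives no decision and adds nothing to the weight of the point.

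**Conclusion.** The point holds: the scenario 1 bullet and column are wrong as written. At the stated spending time the interim boundary is p 0.0105 (Z 2.309), not 0.0122 (Z 2.2504). The final boundary at 375 events is p 0.0222 (Z 2.010), not 0.0212 (Z 2.0289). Relative to the rule, the illustrated interim test is too lenient and the illustrated final test too strict.

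Overall type I error is not inflated as long as one consistent pair of bounds is used. Table 9, the sample size and the planned power are untouched. The conflict matters only if the interim is run with clearly fewer than 309 events. The recalculation rests on the plan's own spending function, one-sided alpha of 0.025, the example's event counts and, for power, a constant HR of 0.7. Because this is a decision threshold for the primary endpoint in an open-label trial, it should be settled before the interim and not left open to choice afterwards.

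**What to change.** Recompute the scenario 1 bullet and table column at t = 296/386:

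- Interim: Z about 2.309, p 0.0105, HR at bound 0.765, P(cross) 0.0105 if HR=1 and 0.776 if HR=0.7.
- Final (375 events): Z about 2.010, p 0.0222, HR at bound 0.813, power 0.929.

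The text points to this correction. If the sponsor in fact intends to spend at a fixed 80% under slow accrual, the printed column can stay, but the rule in Section 3.8.1, the table footnote and the 77% labels must then change. The text gives little support for that reading.

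In either case, correct the scenario 2 final power to about 0.940.

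The cost is one bullet, one table column and one further cell, with no change to trial conduct or to Table 9.

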**FA boundary calculation:**

The alpha spending at the FA is  $\alpha - \alpha_1$ . FA boundary ( $C_2$ ) is solved from  $P(Z_2 \geq C_2, Z_1 < C_1 | H_0) = \alpha - \alpha_1$ , with test statistics  $Z_1$  and  $Z_2$  being multivariate normal and correlations based on observed event numbers.

The table below summarizes the boundary properties of the hypothetical scenarios, together with the planned scenario.

Value	Planned scenario	Hypothetical scenario 1 (events accrue slower)	Hypothetical scenario 2 (events accrue faster)
IA: Month: 21			
Events (I.F.)	309 (80%)	296 (77%*)	320 (80%*)
Z	2.2504	2.2504	2.2504
p (1-sided)	0.0122	0.0122	0.0122
HR at bound	0.7738	0.7698	0.7776
P(Cross) if HR=1	0.0122	0.0122	0.0122
P(Cross) if HR=0.7	0.8123	0.7933	0.8263
FA: Month: 33			
Events	386	375	395
Z	2.0249	2.0289	2.0212
p (1-sided)	0.0214	0.0212	0.0216
HR at bound	0.8135	0.8110	0.8160
P(Cross) if HR=1	0.0250	0.0250	0.0250
P(Cross) if HR=0.7	0.9350	0.9276	0.9339
Information fraction is the minimum of the expected information fraction and the actual information fraction used for the alpha spending calculation. The actual information fraction based on the observed number of events is used for computing correlations needed to derive the group sequential bounds.			

